9.3 PATIENT PERFORMED ASSESSMENTS

Subjective pre-treatment evaluations will be assessed based on the Subjective Global Assessment. Subjects will be instructed to circle their response.

[figure not shown]
9.3.1 SUBJECT GLOBAL ASSESSMENT

The subject global assessment of improvement will be performed during every visit (except baseline) to assess the subject's impression of their overall improvement as compared to baseline. The subject global assessment scale is defined as follows:

Excellent improvement	My lip lesions are completely (100%) gone, except for possibly some residual color change
Marked improvement	My lip lesions are greatly (~75%) improved
Moderate improvement	My lip lesions are definitely (~50%) improved
Mild improvement	My lip lesions are somewhat (~25%) improved
No improvement	My lip lesions are not (0%) improved

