4.0 SCHEDULE OF ASSESSMENTS

	Treatment Phase		Observational Follow-up Phase			
Visit Number	1 Screening	2 Baseline	3	4	5	6 End of Study/ Early Termination Visit
Week(s)	-2-0 weeks	day 0	6 weeks	12 weeks	24 weeks	36 weeks
Informed Consent	Х					
Medical History	Х					
Demographics	Х					
Inclusion/ Exclusion Criteria	х	х				
Concomitant Medications	Х	Х	х	х	Х	х
Physical Exam	Х	х				х
Treatments		х	Х	Х		
Physician Efficacy Assessments						
Comparison of photographs		х	х	х	х	х
Investigator Global Assessment		Х	х	х	Х	х
Subject Efficacy Assessments						
Subject Global Assessment of Improvement		х	х	х	х	х
DLQI		х	х	х	х	х
Physician Safety Assessments						

Page 11 of 32

		Treatment Phase				Observational Follow-up Phase	
Visit Number	1 Screening	2 Baseline	3	4	5	6 End of Study/ Early Termination Visit	
Week(s)	-2-0 weeks	day 0	6 weeks	12 weeks	24 weeks	36 weeks	
Swelling, Vesiculation, Erosion, Erythema, Flaking, Crusting		х	х	х	х	х	
Hyperpigmentatio n		х	х	х	х	х	
Adverse Events		х	х	х	х	х	
Pregnancy Testing ^d	х	х				х	
Subject Safety Assessments							
Redness, swelling, and dryness		х	х	х	х	Х	
Pain (VAS Scale)		х	х	х	х	Х	
Photographs		Х	х	Х	Х	Х	

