9.2 PHYSICIAN PERFORMED ASSESSMENTS

9.2.1 EFFICACY ASSESSMENTS

Primary efficacy will be assessed by the investigator for clearance from baseline (Visit 2) to the end of study (Visit 6; week 36). Clearance will be estimated clinically as minimal (0%-25%), mild (26%-50%), moderate (51%-75%), good (76%-99%), or complete (100%). Clinical photographs will also be taken at Visit 2 to 6. Care will be taken to avoid including any identifying landmarks, such as characteristic tattoos, birthmarks, etc.

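### The Subject Global Assessment has no level for worsening, so subjects whose lip gets worse are recorded together with those who are unchanged

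*Combined protocol and SAP*

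**What the plan says.** Section 9.3.1 states that the Subject Global Assessment is used "to assess the subject's impression of their overall improvement as compared to baseline". It defines five levels. The top one reads "My lip lesions are completely (100%) gone, except for possibly some residual color change", the next "My lip lesions are greatly (~75%) improved", followed by levels at about 50% and about 25%. The bottom one reads "My lip lesions are not (0%) improved". Nothing lies below it. Section 9.3 adds: "Subjects will be instructed to circle their response". The figure that follows that sentence is not available, so the printed form could not be checked against the definition.

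The schedule in Section 4.0 lists "Subject Global Assessment of Improvement" under the subject efficacy assessments and marks it from Visit 2 to Visit 6. Section 9.3.1 leaves baseline out, so the two places disagree about Visit 2. The synopsis does not name the scale as a primary or secondary endpoint.

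Primary efficacy is the investigator's rating. Section 9.2.1: "Clearance will be estimated clinically as minimal (0%-25%), mild (26%-50%), moderate (51%-75%), good (76%-99%), or complete (100"%). That scale has no level below 0% either.

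No section says how the Subject Global Assessment will be summarised or tested. Section 12.1 says only that a biostatistics group will help with the analysis.

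**The concern.** A rating of change from baseline should be able to record change in both directions. Section 5 describes actinic cheilitis as precancerous and mentions recurrence after conventional treatments, and Section 7.4 follows each subject for 24 weeks after the last treatment. Worsening is therefore an outcome that the study should be able to record. There is one arm, so no comparator shares the same floor.

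Two things are at stake. The number of subjects who consider themselves worse cannot be recovered from the scale, whatever summary is used. In addition, a mean improvement score would come out too high if anyone worsened.

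**Working it through.** The documents give no planned figure for this scale (no expected response, worsening rate or summary measure), so there is nothing to reproduce. The check asks what the floor does to each plausible summary.

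**Inputs.** n = 20 (Section 7.2). Lowest level = 0% (Section 9.3.1). The number worsening, k, and the size of worsening, w, are assumptions. I take k = 1, 2 or 4 and w = 25 or 50 points; 25 points is one step of the existing scale.

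**1. Mean.** Each worsened subject is recorded as 0 instead of −w, so the mean is overstated by k × w / n.

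| k | w = 25 | w = 50 |
|---|---|---|
| 1 | 1 × 25 / 20 = 1.25 | 1 × 50 / 20 = 2.5 |
| 2 | 2 × 25 / 20 = 2.5 | 2 × 50 / 20 = 5.0 |
| 4 | 4 × 25 / 20 = 5.0 | 4 × 50 / 20 = 10.0 |

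With k = 0 the overstatement is 0.

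**2. Responder share.** A worsened subject lies below any positive cut-off whether recorded as 0 or as −w. The share at or above 25%, or at or above 75%, changes by 0.

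**3. Median.** With 20 subjects the median is the average of the 10th and 11th ordered values. The floor alters it only if the 10th lowest value is below 0, that is, if at least 10 of 20 subjects worsen.

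**4. Illustration (assumed data).** Five subjects at 100, five at 75, four at 50, two at 25, and four who truly worsened by 50.
- Recorded mean: (500 + 375 + 200 + 50 + 0) / 20 = 56.25.
- True mean: (1,125 − 200) / 20 = 46.25.
- Median: (75 + 50) / 2 = 62.5 both ways.
- Share at or above 75%: 10 / 20 = 50% both ways. Share at or above 25%: 16 / 20 = 80% both ways.

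**5. Chance that the floor matters at all.** If each subject worsens with probability p, the chance of at least one in 20 is 1 − (1 − p)^20. For assumed p of 2%, 5%, 10% and 20% this is 33%, 64%, 88% and 99%.

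**The case against.** A reader might infer that the patient-rated result is biased upward under any summary. The documents do not support that. The scale is ordinal, no section says it will be averaged, and steps 2 and 3 above show that responder shares are untouched and the median nearly always so. Upward bias needs both a worsened subject and a mean-type summary.

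A reader might also infer that errors on this scale run only upward. That is true of the floor but not of the whole scale. Nothing lies between about 75% and 100%, so a subject at 90% who chooses the 75% level is understated by 15 points. Four such subjects in 20 would lower the mean by 4 × 15 / 20 = 3.0 points. The approximate anchors and verbal descriptors do leave such a subject a nearest level, so I would not press this gap as a defect of its own.

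The strongest objection is that worsening can be seen elsewhere. Section 10.2.1 treats worsening of an established condition as an adverse event, photographs are compared over time, and the DLQI is scored from baseline on. This stands in part, since worsening need not go unnoticed. None of these is a direct substitute, however. The DLQI measures quality of life over the past week. Photographs are not the subject's own rating. The adverse event route is uncertain for a lip lesion, because the synopsis describes adverse events as lying outside the treatment area, and Section 10 refers to signs absent at baseline.

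It is also fair to say that the scale is not a named endpoint and that the study is a 20-subject proof of concept. That limits the importance of the point but does not remove it.

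**Conclusion.** The point holds in a limited form. As defined, the scale merges unchanged and worsened subjects and cannot show patient-rated worsening. That much needs no assumption beyond the printed form matching Section 9.3.1.

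Any numerical bias is conditional. If the scale is averaged, the overstatement is 1.25 to 10 points over the assumed range of k and w. It is zero if nobody worsens, zero for responder shares at a positive cut-off, and zero for the median unless at least half the subjects worsen. The worsening rates are illustrative; the documents supply none.

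Because primary efficacy rests on the investigator's clearance rating, the effect on the trial's conclusion is small. The same floor in Section 9.2.1 deserves at least equal attention: that scale carries the primary endpoint, and its lowest band already combines no change with improvement of up to 25%. This is a cheap improvement to an instrument, not a flaw that threatens the study.

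**What to change.** Add a sixth level to the subject form and to Section 9.3.1, for example: *Worse: my lip lesions are worse than before treatment.* Report the number and share of subjects choosing it at each post-baseline visit.

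State that the scale will be summarised as an ordinal distribution (counts and percentages per level) and not as a mean. A single Worse level carries no percentage, so it cannot by itself correct a mean; the ordinal summary avoids that problem.

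Consider a corresponding Worse level for the investigator's clearance scale in Section 9.2.1. In the same edit, reconcile Sections 4.0 and 9.3.1 on whether the subject scale is completed at baseline.

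The cost is one extra line on the form and a minor amendment. Under Section 11.1 a non-administrative amendment needs the investigator's agreement, review by the drug supplier and written IRB/IEC approval before it is implemented.

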9.3.2 PRE & POST-TREATMENT PAIN ASSESSMENT

Subjects will be asked to describe their pain prior to the application of topical Levulan® and immediately after blue or red light illumination using a Visual Analogue Scale (VAS) from 0 to 10, 0 indicating no pain and 10 indicating the worst possible pain. Pain will be assessed at each treatment visit.

9.3.3 DERMATOLOGY LIFE QUALITY INDEX

Subjects will be asked to complete the Dermatological Life Quality Index (DLQI) at every scheduled visit except for screening. These questionnaires should be completed by the subject before any other procedures or assessments are performed. If the subject is physically unable to complete the questionnaires, study personnel/staff may assist

him/her. Relatives and friends of the subject may not under any circumstances assist the subject with the questionnaire. The subject will initial and date his/her entries in the designated area of the Case Report Form (CRF) for each questionnaire. The CRF will serve as the source documentation for this study. The DLQI questionnaire is as follows:

Dermatological Life Quality Index

The aim of this questionnaire is to measure how much your skin problem has affected your life OVER THE LAST WEEK. Please check one response for each question.

Question	Response
1. Over the last week, how itchy, sore, painful, or stinging has	□ 1. Very much
your skin been?	
	□ 2. A lot
	2 A Pul
	□ 3. A little
	□ 4. Not at all
2. Over the last week, how embarrassed or self-conscious have	
	□ 1. Very much
you been because of your skin?	□ 2. A lot
	2.71.00
	□ 3. A little
	□ 4. Not at all
3. Over the last week, how much has your skin interfered with	□ 1. Very much
you going shopping or looking after your home or garden ?	
	□ 2. A lot
	□ 3. A little
	□ 4. Not at all
	⊔ 4. NOt at all
	□ 5. Not relevant
4. Over the last week, how much has your skin influenced the	□ 1. Very much
clothes you wear?	

	□ 2. A lot
	□ 3. A little
	□ 4. Not at all
	□ 5. Not relevant
5. Over the last week, how much has your skin affected any	□ 1. Very much
social or leisure activities?	□ 2. A lot
	□ 3. A little
	□ 4. Not at all
	□ 5. Not relevant
6. Over the last week, how much has your skin made it difficult	□ 1. Very much
for you to do any sport ?	
	□ 2. A lot
	□ 3. A little
	□ 4. Not at all
	□ 5. Not relevant
7. Over the last week, has your skin prevented you from	□ 1. Yes
working or studying?	
	□ 2. No
	□ 3. Not relevant
	□ 1. A lot
If "No", over the last week how much has your skin been a	

problem at work or studying?	□ 2.A little
	□ 3. Not at all
8. Over the last week, how much has your skin created problems	□ 1. Very much
with your partner or any of your close friends or relatives ?	
	□ 2. A lot
	2.4.15.1
	□ 3. A little
	□ 4. Not at all
	1 4. NOT at all
	□ 5. Not relevant
9. Over the last week, how much has your skin caused any	□ 1. Very much
sexual difficulties?	1 1. Very mach
sexual difficulties:	□ 2. A lot
	□ 3. A little
	□ 4. Not at all
	□ 5. Not relevant
10. Over the last week, how much of a problem has the	□ 1. Very much
treatment for your skin been, for example by making your	2.41.4
home messy or by taking up time?	□ 2. A lot
	□ 3. A little
	5. / t actic
	□ 4. Not at all
	□ 5. Not relevant

9.3.4 TWO-DAY POST-TREATMENT TELEPHONE FOLLOW-UP VISIT

Patients will be asked to rate *redness, swelling,* and *dryness* on the scale below. The scales will be read to the patient over the phone.

Redness	Grade 0: None
	Grade 1: Minimal redness, only a little noticeable

	Grade 2: Mild redness, easily noticeable and involving less than 1/3 of the face
	Grade 3: Moderate redness, easily noticeable and involving between 1/3 and 2/3 of the face
	Grade 4: Severe redness, very easily noticeable from a distance, and involving over 2/3 of the face
Swelling	Grade 0: None
_	Grade 1: Minimal swelling, only a little noticeable
	Grade 2: Mild swelling, easily noticeable and involving less than 1/3
	of the face
	Grade 3: Moderate swelling, easily noticeable and involving
	between 1/3 and 2/3 of the face
	Grade 4: Severe swelling, very easily noticeable from a distance,
	and involving over 2/3 of the face
Dryness of Skin	Grade 0: None
	Grade 1: Minimal dry skin, only a little noticeable
	Grade 2: Mild dry skin, easily noticeable and involving less than
	1/3 of the face
	Grade 3: Moderate dry skin, easily noticeable and involving
	between 1/3 and 2/3 of the face
	Grade 4: Severe dry skin, very easily noticeable from a distance,
	and involving over 2/3 of the face

Additionally the subject will be asked the open-ended question, "Have you had any problems since leaving our office after your last appointment?" The study coordinator will then record each subject's response in the appropriate source document.

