5. INTRODUCTION & RATIONALE

Actinic cheilitis is a common precancerous malformation of the lower lip caused by UV radiation. Conventional therapies, such as cryotherapy, topical 5-fluorouracil, Imiquimod, chemical peels, electrodessication, laser ablation, and vermilionectomy are oftentimes successful in the majority of patients. However, these treatments may be expensive, time-consuming, associated with noncompliance, have a high recurrence rate, require local or general anesthesia, and offer risk of unaesthetic scars. There are also numerous adverse side effects associated with the aforementioned treatments; therefore, alternative treatments for the treatment of actinic cheilitis are essential.

In the literature, several reports have shown photodynamic therapy (PDT) to be efficacious in the treatment of actinic cheilitis. Of note, patients in these case reports/series received therapeutic benefit with relatively few PDT treatments, which were associated with minimal cutaneous side effects. PDT is based on the combined use of photosensitizers and photoradiation. Topically applied δ -aminolevulinic acid (ALA) is theorized to be taken up by premalignant cells. Upon irradiation with a light source, photoactivated porphyrins produce singlet oxygen and other potent oxidizers, resulting in cell death. Unfortunately, controlled clinical trials assessing the efficacy of PDT for actinic cheilitis are lacking. As PDT does not appear to have any systemic side effects, if proven efficacious, PDT could be one of the safest treatment options for actinic cheilitis.

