8. TREATMENT & BLUE LIGHT PARAMETERS

8.1 PRE-EXPOSURE SKIN CARE

Subjects will wash their face with CeraVe® Facial Cleanser prior to study treatment. Subsequently, the mixed contents of Kerastick® (see section 8.2) will be applied topically with gloves to the designated target treatment area. After an incubation period of ninety minutes, subjects will wash their face again with CeraVe® Facial Cleanser.

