8.3 LIGHT TREATMENT

8.3.1 BLUE LIGHT TREATMENT

Blue light will be administered to the lips using the BLU-U® blue light (417 nm) PDT illuminator. The prescribed treatment time will be 16 minutes and 40 seconds, which will result in a total light dose of approximately 10 J/cm² delivered at 10 mW/cm². Light exposure will be controlled with a timer. The investigator, subject, and anyone else in the light treatment room will wear appropriate protective eyewear at all times.

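### The two-day telephone scale grades redness, swelling and dryness by share of the face, so a lip-confined reaction scored by the written definitions cannot reach Grade 3 or 4

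*Combined protocol and SAP*

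**What the plan says.** In Section 9.3.4 the subject grades redness, swelling and dryness from 0 to 4 in a telephone call two days after treatment. Grades 0 and 1 have no area condition. Grade 2 requires involvement of less than one third of the face. For redness the next two grades read "Grade 3: Moderate redness, easily noticeable and involving between 1/3 and 2/3 of the face" and "Grade 4: Severe redness, very easily noticeable from a distance, and involving over 2/3 of the face". Swelling and dryness use the same thirds. On delivery the section says "The scales will be read to the patient over the phone", and then "Additionally the subject will be asked the open-ended question", which asks about any problems since the last appointment.

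The rest of the protocol is about the lip. Section 5 describes the disease: "Actinic cheilitis is a common precancerous malformation of the lower lip caused by UV radiation". Section 8.3.1 says "Blue light will be administered to the lips", and under Section 8.1 the drug is "applied topically with gloves to the designated target treatment area". The subject's own improvement scale in Section 9.3.1 is worded on the lip, for example "My lip lesions are greatly (~75%) improved".

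Section 4 lists redness, swelling and dryness under Subject Safety Assessments, marked at Visits 2 to 6. The synopsis (Section 3) gives tolerability as a secondary endpoint. It names pain, adverse events and the physician's local skin reaction grades among its measures, but not the telephone scale.

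**The concern.** The scale uses a denominator much larger than the site where a reaction is expected. In Grades 3 and 4 the noticeability wording and the area wording are joined by 'and', so intensity alone cannot lift the grade. A vivid reaction over the whole treated lip would then be reported under the label 'Mild', or under no grade at all.

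At stake is the description of early tolerability. The call is the only graded rating of these signs at day 2. The physician's scale is completed at clinic visits, and the next visit comes after the time in which Section 7.5 expects reactions to have settled. If the call under-grades a reaction, or grades like reactions differently, no other graded measurement at that time corrects it.

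**Working it through.** No power or sample-size figure is involved and the plan states no figure to reproduce. The check is to read the grade definitions against the treated site.

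**Inputs.** Grade definitions: Section 9.3.4. Site of disease, light and drug: Sections 5, 8.3.1 and 8.1. Assumption: a lip-confined reaction covers a share *s* of the face with 0 < *s* < 1/3. The protocol gives no value for *s*, but the result is the same anywhere in that range.

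**Step 1: the grid as written.** The definitions combine noticeability with area. Read strictly, for each of the three items:

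| Noticeability | Under 1/3 of face | 1/3 to 2/3 | Over 2/3 |
|---|---|---|---|
| None | 0 | 0 | 0 |
| A little | 1 | 1 | 1 |
| Easily | 2 | 3 | no grade |
| Conspicuous from a distance | no grade | no grade | 4 |

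**Step 2: lip-confined reactions.** With *s* < 1/3 only the first area column is available. Grade 3 needs *s* of at least 1/3 and Grade 4 needs *s* > 2/3, so both fail for every admissible *s*. The reachable grades are 0, 1 and 2, which is 3 of 5, on 3 of 3 items. A reaction conspicuous from a distance lands in an empty cell; its closest match by area is Grade 2.

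**Step 3: comparison with the physician scale.** In Section 9.2.2, Grades 3 and 4 for swelling carry no area condition, and no item on that scale refers to the face. A markedly swollen lip can therefore be Grade 4 to the physician, while by telephone it is at best Grade 2.

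**Step 4: changing the denominator alone.** If the same grid is read with thirds of the treated lip, all three columns open and 5 of 5 grades are reachable, but the empty cells stay. An easily noticeable reaction over more than 2/3 of the treated lip, short of conspicuous from a distance, is Grade 2 today and would then fit no grade. A conspicuous reaction over a small part of the lip still fits none.

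**Step 5: whether other records cover day 2.** The next clinic visit is nominally six weeks (42 days) after a treatment. Section 7.5 puts typical resolution at one to two weeks, so by 14 days; 42 − 14 = 28 days later. If the three-day window is read as ±3 days around the Section 4 weeks (an assumption), the shortest gap is Visit 3 to Visit 4: (84 − 3) − (42 + 3) = 36 days, still 36 − 14 = 22 days later. For adverse events, Section 10 limits recording to signs outside the expected profile and names erythema and dryness as anticipated or potential effects. Edema appears only in Section 7.5. Section 10.2.1 defines adverse events more broadly and says all are recorded. The adverse event record is thus an uncertain backup, and the open question yields text rather than a grade.

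**The case against.** The strongest reply is that subjects assign these grades. They hear the words 'Mild', 'Moderate' and 'Severe', and nothing stops a subject with a very red lip from choosing Grade 3 or 4. That stands. A reader might infer that no lip-confined reaction will ever be recorded above Grade 2. The documents do not support that, because the limit binds only when the area wording is followed. The reply does not rescue the scale, however: if some subjects answer by label and others by area, the same reaction receives different grades, and no rule says which reading governs.

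A second reply is that no named endpoint rests on this scale. That also stands. A reader might infer that a secondary endpoint is compromised, but the synopsis does not list the telephone ratings among its secondary or safety measures. Section 4 classes them as subject safety assessments, so they bear on tolerability without being a named endpoint.

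Third, a reader might infer that expected reactions will not be recorded as adverse events. Section 10 points that way, but Section 10.2.1 does not clearly agree, and the point is least certain for swelling.

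Finally, the face wording does capture spread beyond the lip. That is real information, and a lip denominator removes it from the grade.

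**Conclusion.** The point holds for reactions confined to the lips and scored by the written definitions. On each of the three items such a reaction can use 3 of 5 grades, and one conspicuous from a distance strictly has no grade. Apart from the wording of the protocol, this rests only on the lips being less than one third of the face. How many ratings would be under-graded, or graded inconsistently, cannot be computed from the documents.

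The consequence is limited to the day-2 safety description in a 20-subject, single-arm, proof-of-concept study. Primary efficacy, the physician scale, the pain scale and the reasons for discontinuation in Section 7.6 are unaffected. It is still worth correcting, because the rule as written gives a misleading grade for the very site being treated and the correction is nearly free.

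**What to change.** In Section 9.3.4, for all three items, replace the face denominator with the treated lip area, stated as the area to which drug was applied. Grades 2 to 4 of three items make 3 × 3 = 9 definitions to edit. Redraw the grades so that every reaction has exactly one. For example:

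- Grades 0 and 1: unchanged.
- Grade 2: easily noticeable, less than 1/3 of the treated lip area.
- Grade 3: easily noticeable, 1/3 or more of that area.
- Grade 4: the existing Grade 4 noticeability wording, whatever the extent, with Grades 2 and 3 understood to fall short of it.

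This fills the empty cells found in Steps 1 and 4 of the check. Grading by noticeability alone would also work. Record spread beyond the lips under the existing open question.

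The cost is an edit to the telephone script, with no added question, contact or staff. Day-2 grades may be higher, will not be comparable with any ratings already taken on the face wording, and will no longer reflect spread beyond the lips.

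A minor point: the Section 4 row for these ratings marks Visits 2 to 6 and not the two-day call. Reconcile the two, unless a footnote lost from the available text already does so.
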